9.1 Discontinuation and completion

9.1.1 Study treatment discontinuation and study discontinuation

Discontinuation of study treatment for a participant occurs when study treatment is stopped earlier than the protocol planned duration and can be initiated by either the participant or the investigator.

The investigator must discontinue study treatment for a given participant if, he/she believes that continuation would negatively impact the participant's well-being.

Study treatment must be discontinued under the following circumstances:

- Participant/guardian decision
- Pregnancy
- Use of prohibited treatment as per recommendations in the prohibited treatment section
- Any situation in which study participation might result in a safety risk to the participant

If discontinuation of study treatment occurs, the investigator should make a reasonable effort to understand the primary reason for the participant's premature discontinuation of study treatment and record this information.

Participants who discontinue study treatment or who decide they do not wish to participate in the study further should NOT be considered withdrawn from the study UNLESS they withdraw their consent (see Section 9.1.2 'Withdrawal of Informed Consent' section). **Where possible, they should return for the assessments indicated** in the Assessment Schedule. If they fail to return for these assessments for unknown reasons, every effort (e.g. telephone, e-mail, letter) should be made to contact the participant/pre-designated contact as specified in the lost to follow-up section. This contact should preferably be done according to the study visit schedule.

If the participant cannot or is unwilling to attend any visit(s), the site staff should maintain regular telephone contact with the participant, or with a person pre-designated by the participant. This telephone contact should preferably be done according to the study visit schedule.

After study treatment discontinuation, at a minimum, in abbreviated visits, the following data should be collected at clinic visits or via telephone/email contact:

- New / concomitant treatments
- Adverse Events / Serious Adverse Events (including COVID-19 disease)

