- Dose not changed
- Dose Reduced/increased
- Drug interrupted/withdrawn

6. Its outcome (i.e. recovery status or whether it was fatal)

Conditions that were already present at the time of informed consent should be recorded in medical history of the participant.

Adverse events (including lab abnormalities that constitute AEs) should be described using a diagnosis whenever possible, rather than individual underlying signs and symptoms.

Adverse event monitoring should be continued for at least 30 days following the last dose of study treatment.

Once an adverse event is detected, it must be followed until its resolution or until it is judged to be permanent (e.g. continuing at the end of the study), and assessment must be made at each visit (or more frequently, if necessary) of any changes in severity, the suspected relationship to the interventions required to treat it, and the outcome.

Information about adverse drug reactions for the investigational drug can be found in the Investigator's Brochure (IB).

Abnormal laboratory values or test results constitute adverse events only if they fulfill at least one of the following criteria:

- they induce clinical signs or symptoms
- they are considered clinically significant
- they require therapy

Clinically significant abnormal laboratory values or test results must be identified through a review of values outside of normal ranges/clinically notable ranges, significant changes from baseline or the previous visit, or values which are considered to be non-typical in participant with the underlying disease.

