12.3 Treatments

The Safety set will be used for the analyses below. Categorical data will be summarized as frequencies and percentages. For continuous data, mean, standard deviation, median, 25th and 75th percentiles, minimum, and maximum will be presented.

The duration of exposure in days to Ofatumumab will be summarized by means of descriptive statistics using the safety set.

Concomitant medications and significant non-drug therapies prior to and after the start of the study treatment will be listed and summarized according to the Anatomical Therapeutic Chemical (ATC) classification system, by cohort.

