12.5.1 Safety endpoints

For all safety analyses, the safety set will be used. All listings and tables will be presented by cohort.

Safety summaries (tables, figures) include only data from the on-treatment period with the exception of baseline data which will also be summarized where appropriate (e.g. change from baseline summaries). In addition, a separate summary for death including on treatment and post treatment deaths will be provided. In particular, summary tables for adverse events (AEs) will summarize only on-treatment events, with a start date during the on-treatment period (treatment-emergent AEs).

The on-treatment period lasts from the date of first administration of study treatment to 30 days after the last study visit.

Adverse events

All information obtained on adverse events will be displayed by cohort and participant.

The number (and percentage) of participants with treatment emergent adverse events (events started after the first dose of study medication or events present prior to start of double-blind treatment but increased in severity based on preferred term) will be summarized in the following ways:

- by cohort, primary system organ class and preferred term.
- by treatment, primary system organ class, preferred term and maximum severity.
- by treatment, Standardized MedDRA Query (SMQ) and preferred term.

Separate summaries will be provided for study medication related adverse events, death, serious adverse events, other significant adverse events leading to discontinuation, and adverse events leading to dose adjustment.

A participant with multiple adverse events within a primary system organ class is only counted once towards the total of the primary system organ class.

Vital signs

All vital signs data will be listed by treatment group, participant, and visit/time and if ranges are available, abnormalities (and relevant orthostatic changes) will be flagged. Summary statistics will be provided by treatment and visit/time.

Clinical laboratory evaluations

All laboratory data will be listed by treatment group (cohort 1 and 2), participant, and visit/time and if normal ranges are available abnormalities will be flagged. Summary statistics will be provided by treatment and visit/time.

[REDACTED]

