2.1.1 General definitions

Study treatments

The modRNA vaccine and the ofatumumab treatment are defined both as study treatments. The ofatumumab treatment which is started either before or after receiving a SARS-CoV-2 mRNA vaccine (either initial or booster) is considered as treatment of interest.

Screening failure

A screening failure is a patient not eligible for the study. Screening failures are identified by:

- any inclusion criterion is violated or
- any exclusion criterion applies

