5.2 Treatment-emergent adverse events

Treatment emergent AEs are those which start in the on-treatment period. The on-treatment period lasts from the date of first administration of study medication after informed consent to 30 days after the last visit.

The date of first administration of study medication is the date of 1st vaccination or the date of first ofatumumab at or after screening whichever is earlier.

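### The SAP counts treatment-emergent AEs by start date only, omits the required ofatumumab exposure summary, and its cohort AE tables do not separate time on and off ofatumumab

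*SAP*

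**What the plan says.** **Definition.** SAP 5.2 states: "Treatment emergent AEs are those which start in the on-treatment period". SAP 2.9.1 gives the same rule and presents it as the protocol's. Protocol 12.5.1 contains two rules. Its opening text limits the AE tables to events whose start date lies in the on-treatment period. Its paragraph on adverse events also counts "events present prior to start of double-blind treatment but increased in severity based on preferred term".

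**Window.** SAP 5.2: "The on-treatment period lasts from the date of first administration of study medication after informed consent to 30 days after the last visit". The start is fixed as follows: "The date of first administration of study medication is the date of 1st vaccination or the date of first ofatumumab at or after screening". The earlier of the two dates applies. Protocol 12.5.1 sets the same end point.

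**Study treatment.** SAP 2.1.1: "The modRNA vaccine and the ofatumumab treatment are defined both as study treatments". Under SAP 2.2 the safety set takes anyone who received any study drug.

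**Exposure.** Protocol 12.3: "The duration of exposure in days to Ofatumumab will be summarized by means of descriptive statistics using the safety set". SAP 2.4.1 gives the interval between ofatumumab start and vaccination, and the numbers of patients who interrupt or permanently stop by each efficacy time point. It gives no duration.

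**After stopping.** Protocol 9.1.1: "Participants who discontinue study treatment or who decide they do not wish to participate in the study further should NOT be considered withdrawn", unless they withdraw consent. Protocol 10.1.1: "Adverse event monitoring should be continued for at least 30 days following the last dose of study treatment".

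**Declared changes.** SAP section 4 mentions only the efficacy analysis set.

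**The concern.** Safety and tolerability is a secondary objective, and its main output is a set of AE percentages by cohort. Three features make those percentages hard to read.

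- A worsening event may be counted or not, depending on which protocol sentence is followed. The SAP takes the narrower one without saying that there was a choice.
- The protocol promises ofatumumab exposure in days, which is what a reader needs to judge the percentages. The SAP text does not provide it.
- The window takes no account of whether the patient is on ofatumumab. In cohort 1 it opens at vaccination, so reactions to the vaccine before any ofatumumab enter the same table as events on ofatumumab. A patient who stops ofatumumab and stays in follow-up continues to contribute. Subcohorts followed for 12 and 18 months are combined within each cohort.

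**Working it through.** The plan states no figure on this point that could be reproduced. The check is a comparison of texts, followed by day counts.

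**Worsening.** The two rules in Protocol 12.5.1 give different counts for an event that is already present at first study treatment and then increases in severity: the start-date rule leaves it out and the wider rule includes it. SAP 5.2 uses the start-date rule. The documents do not say whether a worsening is entered as a new AE with its own start date. If it is, the SAP rule picks it up; if it is recorded as a change in an existing entry, it does not. The wider rule also refers to double-blind treatment, which does not exist in this open-label study, so it has no usable reference date as written.

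**Exposure.** Start intervals and counts of patients who stop are not a duration. Days on ofatumumab cannot be obtained from the summaries described in SAP 2.4.1.

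**Time before ofatumumab in cohort 1.** Inputs:
- follow-up of 18 months after vaccination 2 (1a) and 12 months after the booster (1b), Protocol section 3
- vaccination interval of 3 or 4 weeks, the examples in Protocol 4.5
- planned ofatumumab start 4 weeks after vaccination, earliest 2 weeks, Protocol section 3
- 6 weeks as the late limit, taken from the intercurrent-event rule in Protocol 2.1
- one month = 365.25/12 = 30.44 days, so 18 months = 548 days and 12 months = 365 days

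Window for 1a = vaccination interval + 548 + 30. Window for 1b = 365 + 30 = 395. Share = days before first ofatumumab dose / window.

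| Case | Days before ofatumumab | Window | Share |
|---|---|---|---|
| 1a, 3-week interval, start at 2 weeks | 21 + 14 = 35 | 599 | 5.8% |
| 1a, 3-week interval, planned start | 21 + 28 = 49 | 599 | 8.2% |
| 1a, 4-week interval, planned start | 28 + 28 = 56 | 606 | 9.2% |
| 1a, 4-week interval, start at 6 weeks | 28 + 42 = 70 | 606 | 11.6% |
| 1b, start at 2 weeks | 14 | 395 | 3.5% |
| 1b, planned start | 28 | 395 | 7.1% |
| 1b, start at 6 weeks | 42 | 395 | 10.6% |

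For a vaccinated cohort 1 patient who never starts ofatumumab, the share is 100%.

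**Time after stopping.** The documents give no discontinuation rate or timing, so the stop times here are assumptions. For a patient who stops at month k and completes follow-up, the days beyond last dose + 30 that still count as on-treatment are (18 - k) months in 1a and (12 - k) months in 1b. In 1a with a 4-week interval this gives 457 of 606 days (75%) for k = 3, 365 (60%) for k = 6 and 183 (30%) for k = 12. In 1b it gives 274 of 395 (69%) for k = 3 and 183 (46%) for k = 6. These figures describe one patient each, not a cohort.

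**The case against.** The strongest reply is that most of this is the protocol's own design. The window comes from Protocol 12.5.1, and the SAP repeats it. Protocol 10.1.1 does not conflict, because 30 days after the last dose is a minimum for monitoring. Both products are declared study treatments and the safety objective is not limited to ofatumumab, so vaccine reactions belong in the tables. The SAP also follows one of the protocol's two definitions, so its statement that it follows the protocol is defensible. All of that stands. A reader might infer that the SAP introduced the window or plainly contradicts the protocol on worsening; the documents support neither.

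A reader might also infer that events cannot be tied to ofatumumab at all. That goes too far. Protocol 10.1.1 records causality and start and end dates for each AE. SAP 2.9.1 plans summaries of related AEs, of AEs leading to discontinuation and of those leading to dose adjustment, and SAP 2.4.1 counts patients who stop. Nor are worsened events lost altogether: severity changes are assessed at each visit, and a serious worsening falls under the SAE definition in Protocol 10.1.2.

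The table shells are not among the documents and might contain an exposure table or a split of relatedness by product. That possibility cannot be excluded, but an analysis that the protocol requires should appear in the SAP text or be accounted for in section 4.

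Finally, splitting every AE table into three periods would give very sparse cells at about 20 patients per cohort. That is a fair limit on the remedy.

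**Conclusion.** The point holds in a limited form. Protocol 12.5.1 has two treatment-emergent definitions that need reconciling, and the SAP silently takes the narrower one. The required summary of ofatumumab exposure in days is absent from the SAP text, and section 4 mentions neither matter. The planned cohort summaries do not separate time before, on and after ofatumumab, and they combine subcohorts with 12 and 18 months of follow-up.

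Pre-ofatumumab time is modest: 8-9% of the window in 1a and 7% in 1b at the planned start, and up to 11.6% and 10.6% if ofatumumab starts 6 weeks after vaccination. These shares assume completed follow-up and the protocol's example vaccination intervals. Time after stopping could be large for a single patient, but the documents give no basis for saying how many patients it affects, so the 30-75% figures should not be read as a cohort effect. The primary and other efficacy results are unaffected. The consequence is that the AE percentages are harder to interpret.

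**What to change.** (a) Use one treatment-emergent definition in Protocol 12.5.1 and SAP 5.2 that includes events increasing in severity after first study treatment, and delete the double-blind wording.

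(b) Add ofatumumab exposure duration in days, by cohort and subcohort, to SAP 2.4.1.

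(c) In SAP 2.9.1, present related AEs separately for ofatumumab and vaccine where causality was recorded by product. In one supplementary table or listing, flag each treatment-emergent AE and SAE as before first ofatumumab dose, from first dose to last dose + 30 days, or later. The main tables can keep the existing window.

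(d) Record any remaining departure from the protocol in SAP section 4.

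The AE dates are already collected (Protocol 10.1.1), and a dosing CRF exists (Protocol 10.1.5), so no new data are needed. The cost is SAP and protocol wording, some programming and slightly longer output, with sparse cells at about 20 patients per cohort.

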5.3 Statistical models

5.3.1 Primary analysis

The primary parameter “T-cell response” is derived from the laboratory data. Patients who have either SARS-CoV-2 reactive INFg-secreting T-cells or SARS-CoV-2 reactive IL-2 secreting T-cells (or both) are classified as responders. The assessment “equivocal” is rated as reactive for this analysis, which is based on observations made during the validation of the assay. It was noticed that the positive control of the ELISpot assay repeatedly provoked lower signals than seen in healthy volunteers, which led to the conclusion that T-cells from MS patients in general show lower reactivity in this assay. Consequently, the cut-offs for “reactive”/“equivocal” and “not reactive” defined by the kit-manufacturer have to be adjusted to these circumstances and results that would be classified as “equivocal” for healthy patients can be considered as signal and hence as “reactive” for MS patients. The following table presents the derivation of T cell response:

		Reactivity to INFg SARS-CoV-2 (quantitative)			
Reactivity towards IL-2 SARS-CoV-2 (quantitative)		reactive	equivocal	Not reactive	Missing value
	reactive	response	response	response	response
	equivocal	response	response	response	response
	Not reactive	response	response	Non-response	Non-response
	Missing value	response	response	Non-response	m.v. (not included in denominator)

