1.2 Purpose

B-cell depleting therapies have in the past been shown to impair the immune response to conventional vaccines. The objective of this study is to assess whether participants treated with monthly s.c. injections of ofatumumab (20 mg) can mount an adequate immune response to the new class of SARS-CoV-2 modRNA vaccines (initial or booster) as measured by humoral and cellular responses. The study will further investigate the maintenance of SARS-CoV-2 specific responses for up to 18 months after the initial vaccination.

2 Objectives and endpoints

Table 2-1 Objectives and related endpoints

Objective(s)	Endpoint(s)
Primary Objective(s) 
 To estimate the proportion of RMS patients having established SARS-CoV-2-specific T cells after receiving a modRNA vaccine (initial vaccination or booster) either before or after starting ofatumumab treatment. 	Endpoint(s) for primary objective(s) 
 Proportion of RMS patients having established SARS-CoV-2-specific T cells as defined by detection of SARS-CoV-2 reactive T-cells, measured by e.g. enzyme-linked immunosorbent spot (ELIspot) assay from T-cells that were stimulated with SARS-CoV-2 peptide mix, either one month after second dose of vaccine or one month after booster vaccine in participants who received the respective vaccine before or after starting ofatumumab treatment (yes/no)
Secondary Objective(s) 
 To estimate the proportion of RMS patients maintaining for up to 18 months SARS-CoV-2-specific T cells after receiving a modRNA vaccine either before or after starting ofatumumab treatment. To estimate the increase in specific T-cells after receiving a modRNA booster vaccine either before or after starting ofatumumab treatment. 	Endpoint(s) for secondary objective(s) 
 Proportion of RMS patients with detectable SARS-CoV-2 reactive T-cells one week, 6, 12 and 18 months after second dose of vaccine or 6 and 12 months after booster vaccine in participants who received the vaccine before or after starting ofatumumab treatment (yes/no) Fold change of SARS-CoV-2 specific T-cell levels one week, 1 month, 6 months, 12 months and 18 months after the second dose of vaccine or 1 months, 6 months and 18 months after a booster vaccine compared to the last timepoint before the respective vaccine

Objective(s)	Endpoint(s)

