2.1 Primary estimands

The primary clinical question of interest is: What is the proportion of RMS patients having developed a specific immune response after receiving a SARS-CoV-2 mRNA vaccine (initial vaccination or booster vaccine) either before or after starting ofatumumab treatment.

The justification for the primary estimand is that it will capture whether ofatumumab-treated patients will mount a specific T-cell response after receiving a SARS-CoV-2 mRNA vaccine assessed by enzyme-linked immunosorbent spot (ELISpot) assays from T-cells that were stimulated with SARS-CoV-2 peptide mix.

Patients will receive either their initial vaccination (1st and 2nd SARS-CoV-2 vaccines) or a booster vaccine before or after starting ofatumumab treatment. In both cases we want to assess if ofatumumab initiation negatively affects or prevents the immune response.

Since this is not a randomized trial, no randomization needs to be preserved and the ITT-principle and the associated estimands framework do not apply. However, this protocol will keep as close as appropriate to the terminology and the definitions established within that framework.

The primary estimand is described by the following attributes:

1. **Population:** Patients with relapsing MS (RMS) divided in two cohorts, each receiving a SARS-CoV-2 mRNA vaccine as part of clinical routine: (1) vaccination before start of ofatumumab treatment, (2) vaccination after having been on stable ofatumumab treatment for at least 4 weeks. The SARS-CoV-2 mRNA vaccine can be either the initial vaccination cycle (for patient that are exposed to the vaccine for the first time; cohort 1a and cohort 2a) or a booster vaccination (for patients that have already completed the initial vaccination cycle; cohort 1b and cohort 2b). Patients in cohort 1a or 2a who fail to receive

their second dose of vaccine for whatever reason will be included in the analysis as non-responders. Patients in cohort 1a and 2a who did receive their second dose of vaccine and patients in cohort 1b and 2b who received their booster shot and do not have a valid determination of specific T-cell response to SARS-CoV-2 for whatever reason will be excluded from the analysis of vaccine efficacy.

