4.1 Rationale for study design

A two-cohort, multicenter, open-label, prospective design has been selected to generate data in a timely manner in order to provide a guidance for physicians and patients on the timing of initial and booster SARS-CoV-2 vaccination and the start of ofatumumab treatment in RMS patients. The study will assess two main questions:

- a) Can patients mount an immune response towards SARS-CoV-2 modRNA vaccines (initial vaccination or booster) when starting ofatumumab treatment after vaccination?
- b) Can patients mount an immune response towards SARS-CoV-2 modRNA vaccines (initial vaccination or booster) when receiving the vaccination while on stable ofatumumab treatment (for at least 4 weeks after the first ofatumumab dosing)?

A non-randomized design has been chosen to enable feasible recruitment as the patient's wish as well as the physician's discretion have to be taken into consideration when deciding on the timing of the vaccine and start of ofatumumab treatment.

Rationale for study population

Initiation and maintenance of ofatumumab treatment in this study will be performed as per approved SmPC. No inclusion/ exclusion criteria regarding age or disease severity were implemented in this study in order to reflect the clinical routine of ofatumumab patients in Germany as closely as possible. Therefore, all patients eligible for ofatumumab treatment and a SARS-CoV-2 modRNA vaccine may be suitable for KYRIOS as long as all other inclusion/exclusion criteria are met. In order to assess whether ofatumumab patients can mount an immune response after vaccination, patients with previous known COVID-19 disease will be excluded from the study.

Rationale for chosen endpoints

Recent publications about the immune responses after vaccination with the new SARS-CoV-2 modRNA vaccines show that both, BNT162b2 (Pfizer/BioNTech) and mRNA-1273 (Moderna), not only induced an antibody-response against the SARS-CoV-2 spike protein but also functional CD4⁺ and CD8⁺ T-cell responses (Jackson, Anderson et al. 2020, Sahin, Muik et al. 2020).

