6.3.2 Treatment assignment, randomization

No randomization will be performed in this study. The assignment of a participant to a particular cohort will be coordinated by the sponsor.

Cohort 1: will be RMS patients receiving modRNA vaccine as part of the clinical routine prior to starting ofatumumab treatment (Cohort 1a: patients that receive their first SARS-CoV-2 vaccination within the study and cohort 1b: patients that have already completed their initial vaccination cycle and will receive a booster vaccine within the study)

Cohort 2: will be participants receiving modRNA vaccine as part of clinical routine while already stable on ofatumumab treatment for at least 4 weeks (since the first dose) (Cohort 2a: patients that receive their first SARS-CoV-2 vaccination within the study and cohort 2b: patients that have already completed their initial vaccination cycle and will receive a booster vaccine within the study).

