12.4.4 Supportive analyses

Patient demographics and baseline characteristics among both cohorts will be compared in the data analysis. Additionally, patients receiving their initial vaccination (cohorts 1a and 2a) vs. a booster shot (cohort 1b and 2b) will be analyzed separately. If patients received a non-mRNA vaccine as booster, this would be reflected in the analysis.

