2. **Variable:** Receiving the second dose of mRNA vaccine (for cohort 1a and 2a) or a booster vaccination (cohort 1b and 2b) and mounting a specific T cell response² one month after second dose of vaccine (cohort 1a and 2a) or booster vaccine (cohort 1b and 2b) defined by detection of SARS-CoV-2 specific T-cells by ELISpot assays after stimulation of T-cells with SARS-CoV-2 peptide mix (yes/no)
3. **Treatment of interest:** ofatumumab treatment, which is started either before or after receiving a SARS-CoV-2 mRNA vaccine (initial vaccination cycle or booster vaccine)
4. **Intercurrent events:**
 - a. Vaccination with a non-mRNA vaccine: patients will be excluded from the study
 - b. Failure to receive the second dose (for cohorts 1a and 2a) of vaccine: patients will be classified as non-responders
 - c. Failure to initiate ofatumumab treatment within six weeks after completion of the vaccination cycle (cohort 1a) or of the booster vaccine (cohort 1b): patients will be excluded from the efficacy analyses

² See appendix 5.3.1 for derivation

d. Failure to complete ofatumumab initiation or interruption of ofatumumab treatment prior to first vaccination (cohort 2a) or prior to booster vaccination (cohort 2b): patients will be excluded from the study

e. No valid detection of SARS-CoV-2 specific T-cells: patients will be excluded from the efficacy analyses if they received their second dose of vaccine (cohorts 1a and 2a) or booster vaccine (cohort 1b and 2b) and further analyses will be performed to confirm methodical reasons

5. **Summary measure:** n.a., there will be no formal comparison between cohorts. Response rates will only be calculated within each cohort.

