2.5.4 Supportive analyses

The reactivity towards SARS-CoV-2 and towards PAN coronaviridae is analysed by frequency tables presenting each investigational visit. This applies to the parameters:

- IFNg (qualitative, i.e. reactive, equivocal, not reactive)
- IL-2 (qualitative, i.e. reactive, equivocal, not reactive)

The stimulation index towards SARS-CoV-2 and towards PAN coronaviridae is analysed by sample statistics and a boxplot graph for each investigational visit. This applies to the parameters:

- IFNg (quantitative)
- IL-2 (quantitative)

If relevant differences in demographic or other baseline characteristics are observed post-hoc analysis will be performed to adjust the primary endpoint for these inhomogeneities. A logistic regression model would be applied.

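### The fold-change endpoint for the booster increase lists an 18-month time point that no subcohort can reach and omits month 12, and no described output pairs baseline with month 1 for the T-cell response in cohorts 1b and 2b

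*SAP*

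**What the plan says.** **Primary endpoint.** Protocol Table 2-1 asks for the proportion of patients "having established SARS-CoV-2-specific T cells after receiving a modRNA vaccine (initial vaccination or booster) either before or after starting ofatumumab treatment", measured one month after the second dose or the booster. SAP 5.3.1 derives it from the ELISpot result at that visit: "Patients who have either SARS-CoV-2 reactive INFg-secreting T-cells or SARS-CoV-2 reactive IL-2 secreting T-cells (or both) are classified as responders". An equivocal result counts as reactive. Baseline plays no part.

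**Booster cohorts.** Protocol 6.3.2 describes 1b and 2b as "patients that have already completed their initial vaccination cycle and will receive a booster vaccine within the study". SAP 2.1.3 gives both a baseline efficacy visit (the screening visit in 1b, the baseline visit in 2b).

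**The question asked.** Protocol 4.1 poses it for cohort 2 as "Can patients mount an immune response towards SARS-CoV-2 modRNA vaccines (initial vaccination or booster) when receiving the vaccination while on stable ofatumumab treatment". Protocol 2.1 justifies the estimand by saying "it will capture whether ofatumumab-treated patients will mount a specific T-cell response after receiving a SARS-CoV-2 mRNA vaccine". The SAP variable reads "or a booster vaccination (cohort 1b and 2b) and mounting a specific T cell response".

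**Planned outputs.** SAP 2.5.4 gives frequency tables of reactivity by visit, for IFNg and IL-2 separately, and adds: "The stimulation index towards SARS-CoV-2 and towards PAN coronaviridae is analysed by sample statistics and a boxplot graph for each investigational visit". Protocol 12.4.4 says that "patients receiving their initial vaccination (cohorts 1a and 2a) vs. a booster shot (cohort 1b and 2b) will be analyzed separately". SAP 2.2.1 shows subcohorts in selected tables.

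**Fold change.** Protocol Table 2-1 and SAP 1.2 attach it to the objective of estimating the T-cell increase after a booster. The post-booster times are 1, 6 and 18 months, and the reference is the last time point before that vaccine. SAP 2.7.1, which sets out the secondary analyses, does not name it.

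**The concern.** A patient who completed an mRNA cycle before entry may already be ELISpot-reactive when the study booster is given. A high month-1 rate in 2b would then fit two accounts: the booster worked under ofatumumab, or the patients were reactive beforehand and stayed so. The objective on booster increase exists to tell these apart, and fold change is its only endpoint.

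That endpoint has an unreachable last time point, lacks a reachable one, and has no line in the analysis section. Followed as written, the plan produces an empty 18-month row and no 12-month row. The described T-cell summaries show each cytokine at each visit, not what happened to individual patients between visits. What is at stake is the reading of the booster results, above all in 2b. The primary rate does not change.

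**Working it through.** **1. The plan's own figure.** SAP section 3 gives 95% half-widths of 20.1%, 19% and 17.5% for n = 20 at response rates of 70%, 75% and 80%. The Wald formula 1.96 × √(p(1−p)/20) gives 20.08%, 18.98% and 17.53%, so these reproduce. They apply to a whole arm; the documents state no size for 1b or 2b.

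**2. Calendar check (Protocol section 3, SAP 2.1.3).** Let B be the booster date, V2 the second vaccination and d > 0 the time from V2 to an optional booster.
- 1b/2b: the study ends at B + 12 months. The listed point is B + 18, and 18 − 12 = 6 months too late. SAP 2.1.3 marks month 18 as not applicable for both.
- 1a/2a: the study ends at V2 + 18 months, so follow-up after the booster is 18 − d, always below 18.
- Month 12 after the booster is a scheduled efficacy visit in 1b/2b. In 1a/2a it falls inside the study only if d ≤ 18 − 12 = 6 months, and no visit is tied to it.
- Protocol 8.3.2 and 12.1, and the other booster endpoints in SAP 1.2, all stop at 12 months.

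**3. What the month-1 rate leaves open.** Neither baseline reactivity nor subcohort size is given, so the following is an illustration. Assume n = 10 booster patients and m = 8 responders at month 1 (exact 95% CI 44.4–97.5%). Let k be the number reactive at baseline, and assume they stay reactive. Response among baseline-non-reactive patients is (m − k)/(n − k):

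| k | New response | Exact 95% CI |
|---|---|---|
| 0 | 8/10 (80%) | 44.4–97.5% |
| 2 | 6/8 (75%) | 34.9–96.8% |
| 4 | 4/6 (67%) | 22.3–95.7% |
| 5 | 3/5 (60%) | 14.7–94.7% |
| 8 | 0/2 (0%) | 0–84.2% |

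**4. Whether the by-visit tables settle k.** With a patients reactive on IFNg and b on IL-2, the composite lies between max(a, b) and min(n, a + b). For a = b = 4 and n = 10 that is 4 to 8. The same two tables therefore fit 4/6 and 0/2.

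**5. Whether composite counts at both visits would suffice.** Without the stay-reactive assumption, new responders lie between max(0, m − k) and min(m, n − k). For k = 6 and m = 8 that is 2 to 4 of 4; for k = 4, 4 to 6 of 6; for k = 8, 0 to 2 of 2. Only a table that pairs the visits within patients fixes the number.

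**The case against.** The strongest reply is that the plan does what it says. Both documents define mounting a response as ELISpot detection (Protocol 2.1, SAP 2.5.1), and Protocol 8.3.1 defines vaccination efficacy as detection at one month. A reader might infer that the responder rule is wrong or the primary rate biased. The documents do not support that: the endpoint is a status, and the rule measures it.

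Three further stronger readings also go too far.
- *Fold change is undefined.* The comparator is named, Protocol 12.5 promises descriptive statistics for every secondary endpoint, and the stimulation index is the only quantitative ELISpot result the SAP summarises (spot counts are only listed). The measure is evident but not stated. A missing baseline is covered, because SAP 2.7.3 leaves missing values unreplaced. Only a zero baseline has no rule.
- *The antibody rule proves an oversight.* SAP 5.3.2 sets baseline-positive patients apart because seroconversion is a change by definition. T-cell detection is not, so the contrast shows a useful model rather than an inconsistency.
- *The SAP certainly contains no paired table.* The table shells are not available and one section is redacted, so this can be said only of what is described.

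The 18-month entry may well be clerical, since other sections stop at 12. It still stands in both documents as an endpoint time. Conversion among non-reactive patients also misses boosting in those already reactive, which fold change captures. That is a reason to read the two together.

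**Conclusion.** The point holds in two parts. First, the fold-change endpoint contains a post-booster time that cannot be observed in any subcohort and omits the 12-month visit of 1b/2b. This rests on the documents' own calendar and needs no assumption. Second, no described output pairs baseline with month 1 for the composite response in patients vaccinated before entry. Their month-1 rate is valid as a status, but alone it does not answer the booster question in Protocol 4.1. This part is limited to the visible text.

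No effect size can be derived; the range from 80% to 0% rests on an assumed 10 patients, 8 responders and no loss of reactivity. The primary analysis stands. The matter is worth correcting because the baseline samples are already planned and the booster objective has no other endpoint.

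**What to change.** Keep the responder rule and the primary analysis.

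1. In Protocol Table 2-1 and SAP 1.2, replace 18 by 12 months as the last post-booster time for fold change.
2. In SAP 2.7.1, report fold change by subcohort as the within-patient ratio of the stimulation index to the last pre-booster sample, for IFNg and for IL-2. State a rule for a zero baseline; a missing baseline stays missing under SAP 2.7.3.
3. Add a supportive baseline-by-month-1 table of the composite response for 1b and 2b, using the SAP 5.3.1 rule at both visits. Show the number already reactive, the number with missing baseline and the month-1 result in the rest, mainly as counts.
4. Read the booster effect from fold change and this table together, with a note that baseline-non-reactive booster patients are a small, selected group.
5. Record the additions in SAP section 4 with their date.

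The cost is wording and a few rows from samples already scheduled; the Protocol line needs an amendment under Protocol 14.1. No primary number changes. There are two downsides. Intervals will be very wide (3/5 gives 14.7–94.7%). The SAP also already cites data notes of 29 September and 20 October 2023, so the new table must be labelled supportive and cannot be presented as planned before data review.
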